## I. Objectives

The study addresses the following FDA Scientific Interest Areas: Chemistry and Engineering, Toxicity, Behavior and Addiction; in that it will determine how specific WP tobacco additives affect users puffing behavior, liking, the quantities of toxicants they inhale and take up into their bodies, and acute pulmonary affects from WP tobacco smoking. These data will inform potential FDA product standards, or maximum limits for additives in WP tobacco, to curb the harm, addictiveness and appeal of WP tobacco smoking. Our multidisciplinary team includes experts in the conduct of clinical trials, WP smoking behavior, WP emissions testing, tobacco product analytical chemistry, psychophysical measurement, and tobacco use risk perception. In the research conducted at The Ohio State University (OSU), we will conduct the study according to the following aims. Note that Aim 3 is the only aim that involves the use of human participants.

Aim 1: Characterize select harmful and potentially harmful constituents (PHHCs) and sugar content of four WP tobaccos (one brand prepared four different ways to vary glycerol and sugars). A commercial WP tobacco brand will be modified to produce four different tobaccos:

- (1) Medium glycerol (60 mg/g), Medium sugars (350 mg/g)
- (2) High glycerol (120 mg/g), Medium sugars (350 mg/g)
- (3) Medium glycerol (60 mg/g), High sugars (510 mg/g)
- (4) High glycerol (120 mg/g), High sugars (510 mg/g)

Aim 2: Characterize select HPHCs and sugars yield in mainstream smoke generated from the four WP tobaccos characterized under Aim 1 using machine smoking of the research-grade waterpipe, and a standardized WP puffing regimen. Hypothesis: Mainstream smoke generated from WP tobacco with higher concentrations of glycerol and sugars will have higher concentrations of HPHCs.

Aim 3: Determine how WP tobacco content impacts puffing behaviors, CO biomarker, pulmonary function, nicotine uptake, and perceived sensory attributes and appeal of WP smoking. Experienced WP smokers will participate in four laboratory sessions to smoke the research-grade waterpipe(s) *ad libitum* using the four different WP tobacco preparations characterized under Aim 1. Hypotheses: Participants will inhale a greater total puff volume and report greater appeal when smoking tobacco with medium glycerol and high sugars; nicotine uptake will not differ across the four tobaccos. Participants will report lower risk perceptions and greater satisfaction when smoking tobacco with medium glycerol and high sugars.

Aim 4: Determine the HPHC exposure ranges from the average puffing behaviors measured under Aim 2 for each tobacco. Topography data collected for all participants for each tobacco type will be averaged to produce four human-derived puffing regimens. Machine smoking will be conducted for each tobacco type, using the associated human-derived puffing regimens, to determine the range of HPHCs in the mainstream smoke. Hypothesis: Toxicant yields will be highest in the mainstream smoke generated from the medium glycerol and high sugars tobacco.

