Currently there are no regulations governing the content of WP tobacco. Because mandated changes in tobacco content may lead to unintended consequences that ultimately result in public health declines, human use behaviors must be well understood prior to implementing regulatory product standards. Compensation, or the degree to which a smoker changes their intake of smoke to make up for the changes made to the tobacco product, is one possible unintended consequence. The proposed smoke HPHC yield measurements, made in smoke generated using both a standardized and a specific (to human-use of the tobacco) puffing regimen, along with the participants' plasma nicotine boost from using the product, will allow us to determine if compensation, and thus greater HPHC exposures, is associated with the presence/absence of sweet additives.

This study will be the first to combine powerful analytical chemistry techniques, CO and nicotine biomarkers, cutting edge psychophysical measurement tools, and risk perception instruments to map the relationship between sensory experiences and preferences of sweetness and flavor to specific additive content in WP tobacco that affect these experiences and preferences. The data from the proposed study will provide direct links between WP tobacco's primary additives, CO and nicotine biomarkers, smoker preferences, perceptions of harm and puffing behaviors, and the subsequent range of HPHC exposures associated with these additives and behaviors. This work will inform the FDA regarding its regulatory authorities surrounding the manufacture, distribution and marketing of WPs, and inform the evaluation of product applications and development of product standards, such as glycerol and sugar content, to reduce the resulting public health toll from WP tobacco product use in the US.

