## III. Procedures

### III.1. Research Design Overview

The proposed study will include preparing and characterizing the content of 4 investigational tobacco products (ITPs) (Aim 1); characterizing the mainstream smoke toxicant emissions from machine smoking the 4 ITPs using a single, established puffing regimen (Aim 2); measuring human puffing behavior, general harm and specific health risk and flavor perceptions, lung function, and biomarkers of exposure in a group of established WP smokers smoking the 4 ITPs in the laboratory (Aim 3), and estimating toxicant exposure ranges using machine smoking and puffing regimens derived from the human laboratory testing (Aim 4).

### AIM 1

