## VII. Data Analysis

### VII.1 Analysis Plan

The main research questions from the four Aims in the proposed study have the same structure for data analysis. That is, there are differences attributable to the four tobaccos in the means of the outcome measures of interest. All relevant outcome variables will be first examined with exploratory/descriptive statistical analyses that focus on describing and understanding patterns and distributions for all relevant measures (e.g., tobacco chemical content, mainstream smoke constituents, spirometry measures, topography measures, psychophysical ratings) by the four tobaccos. We will identify any potential outliers, assess distributional assumptions, and apply appropriate transformations to the outcome variables (e.g., log-transformation) if the normality assumption is violated.

For each of the four aims, the following pairwise comparisons will be performed:

$$H0i j: \mu_i = \mu_j \text{ vs. } H1i j: \mu_i \neq \mu_j$$

where  $\mu_i$  = mean target outcome for tobacco type i, and  $\mu_j$  = mean target outcome for tobacco type j. In Aims 1, 2, and 4, the data will be analyzed using one-way ANOVA models for independent outcome data and Tukey's method will be used to control type-I error rate across the six multiple comparisons. A different analysis strategy will be used in Aim 3 due to the clustered study design: participants will complete four different smoking sessions. Thus, in order to account for the hierarchical design, the data in Aim 3 will be analyzed using linear mixed models containing random subject effects. Since linear mixed models allow for incomplete data (e.g.,

due to dropout), data from all completed smoking sessions will be used in the analysis. As in the other aims, Tukey's method will be used to adjust for multiple comparisons of the tobacco treatments in Aim 3. In addition, for Aim 3, we will use linear mixed models to examine the relationships between the perceived sensory intensity ratings and the liking/disliking ratings for a given tobacco preparation.

Integrating results from Aims 1, 2 and 4 with Aim 3 of the study, the absence or presence, or exposure level of certain HPHCs and other chemical compounds across the different tobacco preparations will be mapped with the data on perceived sensory intensity such as sweetness and liking/disliking ratings.

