## VII.2. Sample Size Justification.

Since Aims 1, 2, and 4 do not involve human subjects, we expect low variability across replicates. Thus, assuming a somewhat conservative coefficient of variation (CV) of 20% and log-normal outcomes, a total of **4 replicates per tobacco preparation** will provide 80% power to detect a two-fold change in the geometric means of two groups at a conservative two-sided Bonferroni-corrected type-I error rate of 0.0083.

Our sample size for Aim 3 was selected to ensure that we have adequate power to detect moderate effect sizes in our comparisons of topography outcomes. We made the following assumptions for the power analysis:

- Based on the intravariability data analysis for the RWP, correlation coefficients within subjects ( $r$ ) were assumed to be 0.6, 0.7 or 0.8.
- Small, medium, and large effect sizes ( $d$ ) of 0.2, 0.5, and 0.8 standard deviations.
- A two-sided, Bonferroni corrected type-I error rate of 0.0083.

Our power analysis, summarized in Table VII-5, revealed that a sample size of 43 subjects will provide over 80% power to detect a moderate effect size unless the within pair correlation is high (0.2 or 0.3) and the within participant correlation is modest (0.6). However, since this power analysis assumes complete follow-up, we will recruit **60 participants** to account for a possible attrition rate of 20%, and ensure the Latin square ordering is balanced across the four tobacco types.

Table VII.5. Estimated % power to for pairwise comparisons of tobacco preparations based N = 25 pairs (50 subjects).

$r$	$\rho$	Power		
		$d=0.2$	$d=0.5$	$d=0.8$
0.6	0.1	0.108	0.803	0.998
	0.2	0.097	0.759	0.996
	0.3	0.088	0.717	0.994
0.7	0.1	0.153	0.918	> 0.999
	0.2	0.138	0.889	> 0.999
	0.3	0.125	0.857	0.999
0.8	0.1	0.255	0.989	>0.999
	0.2	0.228	0.981	>0.999
	0.3	0.207	0.971	>0.999

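### Aim 4 promises exposure ranges for each tobacco but machine-smokes one averaged regimen per tobacco, so its replicates show machine error and not the spread across smokers

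*Combined protocol and SAP*

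**What the plan says.** Section I (Objectives) states Aim 4 as "Determine the HPHC exposure ranges from the average puffing behaviors measured under Aim 2 for each tobacco". Topography from all participants "will be averaged to produce four human-derived puffing regimens", one per tobacco, and machine smoking with those regimens is then used "to determine the range of HPHCs in the mainstream smoke". Section III.1 repeats the promise of exposure ranges from human-derived regimens. Section II.7 says the study will link additives and puffing to "the subsequent range of HPHC exposures associated with these additives and behaviors".

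No percentile, light or heavy, or individual regimen is described, and Section III has no Aim 4 procedures subsection.

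Section VII.1 gives the analysis: "In Aims 1, 2, and 4, the data will be analyzed using one-way ANOVA models for independent outcome data", with Tukey adjustment over six pairwise comparisons. Section VII.2 sizes the machine work at 4 replicates per tobacco. Its reason is that these aims have no human subjects, so "we expect low variability across replicates". It assumes a CV of 20%, which it describes as somewhat conservative. Human variation is modelled only in Aim 3, through random subject effects.

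A side point for correction: Aim 4 attributes the puffing data to Aim 2, which has no participants. Topography is collected in Aim 3.

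**The concern.** There are two issues, of unequal weight.

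**The range.** Averaging removes the differences between smokers before any smoke is generated. What remains within a tobacco is variation between repeat runs of the same regimen. A minimum-to-maximum over four such runs could be reported as an exposure range when it is measurement noise. The results are meant to inform product standards, and the exposure of heavier users is what a range should reveal.

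**The error term.** Each regimen is an estimate from about 50 people, but the ANOVA takes it as known. If a difference in yield is read as a difference between smokers of two tobaccos, the standard error omits the sampling error of the mean regimens.

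**Working it through.** **Inputs from the documents.** Machine CV 20%, log-normal outcomes, 4 replicates, a two-fold change and two-sided alpha 0.0083 (Section VII.2); about 50 complete participants (III.B3); within-subject correlation r of 0.6 to 0.8 (VII.2, for Aim 3); four tobaccos and Tukey adjustment (VII.1).

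**Assumed.** Between-smoker CV of puffing 40 to 80%, and yield proportional to puff volume within a tobacco. The documents give neither.

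**1. The plan's replicate number.** Log-scale SD = sqrt(ln(1 + 0.20²)) = 0.198, and the two-fold difference is ln 2 = 0.693. The noncentrality with n = 4 is 0.693 / (0.198 × sqrt(2/4)) = 4.95. A two-sample t test on 6 df then has power 0.80 (0.46 at n = 3). The stated 4 replicates reproduce, with 20% acting as replicate error alone.

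**2. Spread the replicates can show.** At CV 20%, the median ratio of largest to smallest of 4 runs is 1.48. All of it is machine and assay error.

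**3. Spread removed by averaging.** The 10th to 90th percentile span is exp(2 × 1.2816 × s), where s = sqrt(ln(1 + CV²)).

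| Assumed puffing CV | s | 10th–90th percentile span |
|---|---|---|
| 40% | 0.385 | 2.7-fold |
| 60% | 0.555 | 4.1-fold |
| 80% | 0.703 | 6.1-fold |

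**4. Effect on the ANOVA.** The error in a log mean regimen that matters for contrasts is s × sqrt((1 − r)/50).
- Smallest case (CV 40%, r 0.8): 0.385 × sqrt(0.2/50) = 0.024.
- Largest case (CV 80%, r 0.6): 0.703 × sqrt(0.4/50) = 0.063.

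The machine error of a mean of 4 runs is 0.198/2 = 0.099. The true standard error therefore exceeds the ANOVA's by sqrt(1 + (0.024/0.099)²) = 1.03 up to sqrt(1 + (0.063/0.099)²) = 1.19.

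Tukey familywise error with no true difference was simulated with 40,000 draws per setting and q(4,12) = 4.20, against a nominal 5%:

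| Machine CV | SE understated by a factor of | Familywise error |
|---|---|---|
| 20% (the plan's figure) | 1.03–1.19 | about 6–11% |
| 10% (assumed) | 1.11–1.61 | 8–30% |
| 5% (assumed) | 1.40–2.71 | 20–70% |

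**5. A tempting repair that fails.** Suppose each participant's volume is multiplied by the tobacco's yield per litre and the products go into the Aim 3 mixed model. The error in yield per litre is shared by everyone who smoked that tobacco, so a random subject effect cannot detect it. At machine CV 20% the standard error is then understated by sqrt(1 + (0.099/0.063)²) = 1.9 up to sqrt(1 + (0.099/0.024)²) = 4.2. Simulated familywise error (Tukey, 147 df) is about 50 to 92%, far worse than the plan's own ANOVA.

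**The case against.** The strongest defence is that Aim 4 asks an emissions question. Its hypothesis concerns yields in smoke, the aim itself says it works from average behavior, and Section II.7 pairs a standardized regimen with a human-derived one to look for compensation. Comparing yields at four mean regimens serves that purpose, and the plan does not claim that the ANOVA describes individual smokers. That stands, so the ANOVA needs its scope stated and need not be replaced.

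It can also be said that the range means the span across the four tobaccos, or from standardized to human-derived regimen. The wording leaves some room for this, but it fits poorly with ranges for each tobacco and with exposures tied to behaviors.

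Human variation is also not absent from the study. Aim 3 measures carbon monoxide boost, nicotine boost and topography for each person and tobacco. The gap is in the smoke constituents measured only by machine, such as carbonyls and furans.

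A reader might infer that the Aim 4 ANOVA will often declare chance differences to be tobacco effects, in 20 to 70% of null cases. The documents do not support this. That range needs a machine CV of 5% together with the assumed puffing CVs. The only machine CV given is 20%, and calling it somewhat conservative does not establish a value one quarter as large.

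**Conclusion.** The point holds in two parts. The main one is that the procedure described yields each tobacco's emissions at mean puffing, with machine error, and not a range of exposure across smokers. This follows from the text and needs no assumed figure. Its practical size, a 2.7- to 6.1-fold percentile span, rests on the assumed puffing CV of 40 to 80% and on proportionality.

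The second part is minor. The ANOVA is conditional on four estimated regimens. As a statement about smokers, it has a familywise error of about 6 to 11% at the plan's 20% machine CV, with the same assumed puffing CVs, r of 0.6 to 0.8 and 50 participants. The excess becomes large only if machine CV is well below 20%. The replicate calculation is not in error.

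It would go too far to conclude that Aim 4 has no valid use or that its ANOVA is wrong for emissions. The change is worth making because the promised range can be had from data already being collected.

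**What to change.** - **Report a range.** Keep the machine runs. For each tobacco, multiply the measured yield per litre by each participant's own total puff volume in that tobacco's session (Section IV already records puff volume). Report the 10th, 50th and 90th percentiles as the exposure range.
- **Carry both errors in any between-tobacco comparison about smokers.** For example, bootstrap participants, keeping each person's four sessions together, jointly with machine replicates. With only 4 runs, plain resampling understates the machine SD by sqrt(3/4) = 0.87, so rescale the residuals or pool them over the four tobaccos. Do not rely on the Aim 3 mixed model alone for the scaled values.
- **State the scope of the ANOVA.** Say that it compares yields at four fixed mean regimens only.
- **Correct the wording.** Define what the range means, and attribute the topography to Aim 3.

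The cost is analysis time and text, with no extra runs or visits. The downside is the assumption that yield is proportional to puff volume within a tobacco. Comparing yield per litre under the Aim 2 and Aim 4 regimens checks this in part, but coarsely. With 4 runs each at CV 20%, the log ratio has standard error 0.198 × sqrt(2/4) = 0.14, so 95% limits (t on 6 df, 2.45) are about 1.4-fold either way for one tobacco.

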## II. Background and Rationale

The scientific premise of this study includes understanding who smokes waterpipe, how the harm of using a tobacco product is codified by the FDA, and how sweet WP tobacco additives may contribute to the harm of WP tobacco smoking.

### II.1. Who Smokes Waterpipe?

Just within the past 16 years, the global spread of waterpipe (WP) tobacco smoking has exceeded predictions. This worldwide epidemic has increasingly spread among youth, primarily in the Middle East and North Africa. During 2011-2014, U.S. middle and high school student use substantially increased each year with an estimated 1.6 million adolescent WP users. Longitudinal studies indicate the majority of experimentation begins in high school and early college, with up to 13.8% never-users initiating WP in the first month of college. Because of inconsistent indoor air legislation across the U.S., hookah lounges that support and thrive on early social experimentation with WP and other combustible tobacco products are prevalent near college campuses. The 1990s introduction and widespread availability of heavily sweetened WP tobacco, and the persistent perception that WP usage is a safer alternative to cigarette smoking, are thought to be two of the main contributing factors leading to the rise in popularity of WP tobacco smoking among youth. As cigarette smoking declines, more novel tobacco products that contain sweet flavors that mask the harshness of tobacco smoke are the products most often tried by youth.

### II.2. How Do We Codify Harm?

The U.S. Food and Drug Administration (FDA), through the Family Smoking Prevention & Tobacco Control Act, classifies harm from tobacco products in terms of the chemical constituents that can be inhaled, ingested, or absorbed into the bodies of users. These harmful and potentially harmful constituents (HPHCs) have been measured in WP tobacco smoke, and thus have the potential to cause direct harm via delivery of carcinogens, pulmonary, cardiovascular and developmental toxicants, and addictive chemicals to the body, or indirect harm by facilitating tobacco initiation, increasing progression to cigarette smoking, impeding cessation of cigarette smoking, and/or increasing the intensity of tobacco product use.

### II.3. How Can Sweet WP Tobacco Additives (Sugars and Glycerol) Contribute to Direct Harm?

WP tobacco smoking is associated with increased risk for lung, oral, esophageal, and head and neck cancers, and cardiovascular and pulmonary disease. Despite its growth in popularity over the past 30 years, there is little data available on the ingredients in WP tobacco, as the bulk of research has focused on toxicant yields in the smoke that is inhaled. WP tobacco is very different from cigarette or even pipe tobacco in that initial reports show that sweet tasting additives such as sugars and glycerol can comprise up to 70% of WP tobacco by weight.

Glycerol, which is not a sugar but still tastes sweet, can comprise 23–63% of the weight of the tobacco. Sugars such as sucrose, glucose, and fructose can also make up more than a third of WP tobacco weight. These same compounds are added to cigarettes, but at much lower levels (1-5%), to impart “smoothness” to the smoke and act as moisturizing agents, preservatives and solvents for flavor application. During the heating process, these sweet additives form volatile carbonyls, compounds that are known carcinogens and pulmonary toxicants such as acrolein, formaldehyde (IARC Group 1 carcinogen) and acetaldehyde (IARC Group 2B). During smoking, glycerol can dehydrate to acrolein; thus it is not surprising that, given WP tobacco is heavily fortified with glycerol, acrolein levels in WP smoke exceed those in cigarette smoke by a factor of 15 (see Table 3). Acrolein is ciliotoxic and can inhibit both the immune system and lung clearance. When heated, glycerol can also produce formaldehyde and acetaldehyde, which are both contributors to lung cancer in cigarette smokers and chronic obstructive pulmonary disease. Moreover, acetaldehyde increases the abuse liability of nicotine, contributing to the addictiveness of tobacco smoke. Short-term effects from exposure to these carbonyls results in pulmonary irritation and edema. After their authorities were extended to more novel tobacco products like WP, FDA proposed adding glycerol to the HPHC list.

Semivolatile furans, including furfuryl alcohol (FFA), furfural, and 5-hydroxymethylfurfural (HMF), are another group of carcinogens and respiratory toxicants, that are substantially more abundant in mainstream WP smoke than cigarette smoke (see Table 3) due to the abundance of added sugars in WP tobacco. Simple sugars are comprised of molecules that contain six carbon atoms (hexoses) and five carbon atoms (pentoses). Hexoses can be chemically transformed via thermal dehydration into 5-(hydroxymethyl)-2-furaldehyde (HMF). Similarly, pentoses can be thermally dehydrated into furfural. Concerningly, there are few data available regarding the toxicological implications of acute and chronic human inhalation of these compounds. In long-term inhalation studies, FFA (IARC Group 2B) showed carcinogenic activity in the noses of male rats, and the kidneys (renal tubules) of male mice. Furfural shows carcinogenicity in experimental animals via oral administration, but is classified as an IARC Group 3 carcinogen due to the inadequacy of human evidence. However, FDA Center for Tobacco Products considered existing evidence strong enough to propose furfural also be added to the HPHC list. Humans can metabolize both HMF and FFA to form genotoxic and mutagenic compounds (5-sulfoxymethylfurfural and furfural sulphate, respectively) in the body via sulfotransferase enzymatic activity. For this reason, WHO has recommended HMF be given high priority for carcinogenic evaluation.

